5.3. Methods to Manage Missing Data

Unless otherwise specified, missing items for observations on the individual items of the derived efficacy and health outcome scales will be handled as follows. If more than 20% of the items are missing, the total scores for these scales will be considered missing. If 20% or fewer items are missing, the average of the available items will be multiplied by the total number of items to get a derived total score. Similarly, if more than 20% of the items from a subscale are missing the subscale will not be used in the analysis. If 20% or fewer items are missing then the average of the available items for that subscale will be multiplied by the total number of items in the subscale to get the derived subscale score.

Where an observed case analysis is being employed, the data will be analyzed without imputation for missing visit data. Where the last observation carried forward (LOCF) approach is being employed, efficacy assessments will be handled in the following manner. If the scheduled assessment is available it will be used. If the scheduled assessment is missing, the immediately preceding assessment, scheduled or unscheduled, will be used (eg, if assessments are to be done at weeks 4, 8 and 12 and data are available at weeks 4 and 12 but week 8 is missing, then the week 4 value will be carried forward to week 8). Baseline data will not be carried forward unless otherwise noted. For composite endpoints, missing components will not be carried forward to complete a composite endpoint with partial data available; only the complete composite endpoint value will be carried forward.

Missing values for safety endpoints will not be imputed.

6. ANALYSES AND SUMMARIES

6.1. Primary Endpoint(s)

6.1.1. ASDAS flare

6.1.1.1. Primary Analysis

Endpoint: ASDAS flare (ASDAS ESR greater than or equal to 2.1).

- Analysis time points: Period 2 (over entire period).
- Analysis population: Period 2 FAS.
- method of imputation for missing data: LOCF.
- Primary analysis methodology: Descriptive summary only of proportion flared at each period 2 visit.

Reporting results:

- Descriptive: proportions (n/N) and 95% Confidence interval) at each period 2 visit.

- Supporting objective and Decision rule: Primary Objective.

Additional analyses for primary endpoint

- Method of imputation for missing data: None .
- Analysis methodology: Kaplan Meier estimate of time to flare and Cox proportional hazards model for evaluation of covariates and estimation of hazard compared to prior study B1801031 which had no withdrawal of treatment.
- Supporting objective and Decision rule: Primary Objective.
- Covariates used (Cox model): Covariates for the Cox regression model of time to flare will include, in addition to study (B1801031 vs B1801381), age, sex, geographic region, baseline CRP (normal vs. high), baseline MRI status (negative vs. Positive), disease duration, prior NSAID response (good vs. not) plus ASDAS values at weeks 12 and 24 or, in a separate model, sustained ASDAS inactive disease in period 1, defined as ASDAS ESR<1.3 at Week 12 or Week 16 (where ASDAS may not be greater than 2.1 at either time point) and at Week 24. Binary variables with small frequencies in either study will not be included in the Cox regression model.

Reporting results:

- Estimation:

Kaplan-Meier estimates of 25%, median and 75% survival and 95% confidence intervals.
Cox model based hazard ratio estimates for covariates and study.
- Tables: Present table with just HR and CI for “study” for 4 models:
 1. study only
 2. study plus baseline variables
 3. study plus baseline variables plus ASDAS continuous at 2 times
 4. study plus baseline variables plus sustained ASDAS remission
- Figures:

Kaplan Meir plots showing both studies flare events.

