#### **2.2.1. Primary Endpoint**

- The primary endpoint is the occurrence of flare (defined as an ASDAS ESR greater than or equal to 2.1) within 40 weeks following withdrawal of ETN.

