### 3. STUDY DESIGN

This multicenter, open-label, three period study will evaluate withdrawal and retreatment of ETN in subjects with nr-ax SpA who achieved an adequate response, as measured by ASDAS CRP less than 1.3 (inactive disease) following 24 weeks of treatment. The study is expected to randomize approximately 200 subjects in Period 1, in order to have approximately 96 subjects qualify for Period 2.

#### 3.1. Period 1

This is an open-label, 24-week period in which all eligible subjects with nr-ax SpA will be enrolled and treated with ETN 50 mg once weekly plus a stable background NSAID at the optimal tolerated anti-inflammatory dosage as determined by the investigator. The target for this period is therapeutic response defined as achieving Ankylosing Spondylitis Disease Activity Scale C-reactive protein (ASDAS CRP) less than 1.3 at Week 24. Subjects who qualify at Week 24 will enter Period 2 after all Period 1 procedures are completed. Subjects who do not achieve ASDAS CRP less than 1.3 will not enter Period 2 and will complete the study following the Week 28 day follow-up phone call/visit.

#### 3.2. Period 2

The Week 24 visit ends Period 1 and marks the beginning of Period 2. This is a 40-week withdrawal period where subjects will discontinue ETN following the Week 24 dose, yet maintain the background NSAID. If the subject has not flared by the Week 64 visit, their participation in the study is complete.

#### 3.3. Period 3

Subjects who flare (defined as an ASDAS ESR greater than or equal to 2.1) during Period 2 will enter a retreatment period and receive approximately 12 weekly doses of open-label ETN. Subjects experiencing increased disease activity can come into the office any time for an evaluation; if flare criteria are met, open-label ETN is started at this unscheduled visit. If the subject has experienced increased disease activity during Period 2, but does not meet the protocol defined criteria for flare, it is the investigator's judgment to determine if the subject should remain in the study or discontinue the study to pursue alternative treatment.

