### **6.5. Re-Treatment Period for Subjects in the Withdrawal Phase (Period 3)**

Subjects in the withdrawal period (Period 2) who experience disease flare will be seen for a re-treatment assessment visit at the study site, which should occur as soon as possible after disease flare. The first visit of the Retreatment period (Period 3) may occur at the same time as a regularly scheduled visit during Period 2 or it may occur as an unscheduled visit. Subjects requiring re-treatment (based on a protocol-defined flare of ASDAS ESR greater than or equal to 2.1) will be offered the option to enter re-treatment (Period 3) and receive 12 weekly doses of open-label ETN (50 mg).

Subjects who discontinue (eg, for an adverse event) at any time are ineligible to enter the re-treatment phase.

Subjects who are eligible to enter the re-treatment period will have the following assessments performed at all visits during the re-treatment period unless otherwise indicated:

- Review concomitant medications including NSAIDs, DMARDs, and corticosteroids at every visit.
- Vital signs including sitting BP and pulse at every visit.
- Physical examination (performed by a physician) at Week R12.

- Measure height (cm) and weight (kg) at Week R12.
- Review of any AEs at every visit that occurred since the previous visit.
- Collect samples for the following laboratory evaluations:
  - Hematology and blood chemistry at Weeks R0 and R12;
  - hsCRP and ESR at every visit;
  - Urine pregnancy test at every visit.
- Confirm and document at every visit the subject is using a highly effective method of birth control.
- MRI of spine and SIJ at Weeks R0 and R12.
- Joint assessment including MASES (enthesitis) and dactylitis evaluation at Weeks R0 and R12.
- Assessment of IBD, psoriasis and uveitis at every visit.
- BASDAI, BASFI, PGA, SA DA, Subject Nocturnal and Total Back Pain Assessment and WPAI at every visit.
- BAS-G, EQ-5D and SF-36 at Weeks R0 and R12.
- Dispense IP and IP diary card at Weeks R0, R4, and R8.
- Collect and review IP diary at Weeks R4, R8, R12.
- Collect IP and complete IP return and accountability document at Weeks R4, R8 and R12.

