#### **9.2. Efficacy Analysis**

##### **9.2.1. Analysis of the Primary Endpoint**

The primary endpoint, the occurrence of flare (ASDAS ESR greater than or equal to 2.1) in Period 2 will be summarized descriptively as the percent with flare with 95% confidence interval. This estimate will include all subjects who qualify for the retreatment interval and have at least one evaluation after treatment is withdrawn.

ASDAS is calculated from the following parameters:

1. Total back pain (BASDAI question 2);
2. Subject global assessment of disease activity;
3. Peripheral pain/swelling (BASDAI question 3);
4. Duration of morning stiffness (BASDAI question 6);
5. C-reactive protein (CRP) in mg/litre or ESR in mm/h.

The ASDAS score is then calculated as follows:

ASDAS CRP = (0.121 x total back pain) + (0.110 x subject global) + (0.073 x peripheral pain/swelling) + (0.058 x duration of morning stiffness) + (0.579 x Ln(CRP+1)).

ASDAS ESR = (0.08 x total back pain) + (0.11 x subject global) + (0.09 x peripheral pain/swelling) + (0.07 x duration of morning stiffness) + (0.29 x  $\sqrt{\text{ESR}}$ ).

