Appendix 2.3. Analysis Intervals For Efficacy And Other Endpoints

Induction (Baseline – Week 24)/ Withdrawal (Week 28-64) / Retreatment (R0-R12) treatment period intervals

| | Target week | Target day | BASDA, BASFI, SADA, VAS PGA, WPAI | Joint Assessment, BAS-, EQ-5D, SF-36 | Hematology/ Blood Chemistry | Urine | Height/Weight |
|----------|-------------|------------|--------------------------------------|--------------------------------------|--------------------------------|------------|----------------------|
| Baseline | | 1 | <=1 | <=1 | | <=1 | <=1 |
| Week 4 | 4 | 28 | 2-42 | | | | |
| Week 8 | 8 | 56 | 43-70 | | | | |
| Week 12 | 12 | 84 | 71-98 | 2-98 | 2-98 | | |
| Week 16 | 16 | 112 | 99-140 | | | | |
| Week 24 | 24 | 168 | 141-182 (or EOS1) * | 99-182 (or EOS1) * | 99-182 (or EOS1) * | | 2-182 (or EOS1) * |
| Week 28 | 28 | 196 | 183-210 | | | | |
| Week 32 | 32 | 224 | 211-252 | 183-252 | | | |
| Week 40 | 40 | 280 | 253-308 | | | | |
| Week 48 | 48 | 336 | 309-364 | 253-364 | | | |
| Week 56 | 56 | 392 | 365-420 | | | | |
| Week 64 | 64 | 448 | 421-EOS2 | 365-EOS2 | 183-EOS2 | 2-EOS 2 | 183-EOS2 |
| Week R0 | 1*** | 1 | <=1 | <=1 | <=1 | | |
| Week R4 | 4 | 28 | 2-42 | | | | |
| Week R8 | 8 | 56 | 43-70 | | | | |
| Week R12 | 12 | 84 | 71-EOS3 | >=2 | >=2 | | >=1 |

*For subjects not entering the withdrawal period, no data should be assigned to periods 2 or 3.

*** Day 1 is relative to the first day in Retreatment Period.

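### The primary endpoint is any flare within 40 weeks, but the SAP tabulates flare visit by visit with LOCF, writes no ever-flare derivation, names no single primary estimate, and is inconsistent about which period owns the pre-dose R0 assessment

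*SAP*

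**What the plan says.** **Endpoint and protocol analysis.** Protocol 2.2.1 defines the primary endpoint as occurrence of flare "within 40 weeks following withdrawal of ETN", a yes/no outcome per subject over a period. Protocol 9.2.1 says that it "will be summarized descriptively as the percent with flare with 95% confidence interval", which is one number.

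**SAP analysis.** SAP 6.1.1.1 sets the time point as the whole of Period 2, the population as the Period 2 FAS and the imputation as LOCF. Its method line reads "Primary analysis methodology: Descriptive summary only of proportion flared at each period 2 visit", and its reporting line again asks for n/N and a 95% CI per visit. Period 2 has six scheduled visits after Week 24 (Weeks 28, 32, 40, 48, 56 and 64).

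**Missing-data rule.** SAP 5.3 states for LOCF: "If the scheduled assessment is available it will be used". Only when the scheduled value is missing is the immediately preceding assessment used, and that may be an unscheduled one.

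**Flares between visits.** Under Protocol 3.3, a subject may attend at any time, and "if flare criteria are met, open-label ETN is started at this unscheduled visit". The Schedule of Activities makes R0 the first visit of Period 3 and allows it to be unscheduled. Protocol 6.5 says that flared subjects "will be offered the option to enter re-treatment (Period 3").

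**Where R0 belongs.** Appendix 2.3 is headed "Withdrawal (Week 28-64) / Retreatment (R0-R12) treatment period intervals". SAP 3.4 and 5.2.2, however, take the Period 3 baseline from the last Period 2 value before retreatment, and Appendix 2.1 places the triggering flare in the withdrawal period.

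**The concern.** A proportion in flare at a visit and a proportion that has ever flared are different quantities. They coincide at Week 64 only if every flare persists in the data up to that row. The SAP leaves that to LOCF and to an unstated decision about R0, so two programmers could each comply with it and report different primary results.

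There are two ways in which a real flare might not reach the Week 64 row:

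- **R0 excluded from Period 2.** For a flare found at an unscheduled visit, the last Period 2 value is then an earlier one below 2.1, and LOCF carries that forward. A subject whose only post-withdrawal evaluation is R0 could also fall outside the Period 2 FAS (SAP 4.1.2).
- **Scheduled value overrides.** If a subject flares, does not enter Period 3 and later has a scheduled ASDAS ESR below 2.1, the scheduled-first rule shows that subject as not flared.

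This is an estimation study whose main result is one proportion, so its definition needs to be fixed in advance.

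**Working it through.** **Inputs.** Protocol 9.1: about 96 subjects enter withdrawal, 70% are expected to flare, and the 95% CI half-width is about 10%. SAP 5.1: two-sided 95% intervals. No document gives the share of flares found only at unscheduled visits, so that share is an assumption, shown as a range.

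**Step 1: reproduce the plan's precision.** Half-width = 1.96 × √(p(1−p)/n) = 1.96 × √(0.70 × 0.30 / 96) = 0.0917, or 9.2 points. Other standard methods give 9.0 (Wilson), 9.6 (Clopper-Pearson) and 9.7 points (Wald with continuity correction). All agree with the stated figure of about 10%.

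**Step 2: planning case with every flare counted once.** 0.70 × 96 = 67.2, so 67 flares; 67/96 = 69.8% (Clopper-Pearson 59.6% to 78.7%).

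**Step 3: R0 read as a Period 2 value.** A subject who flares and starts Period 3 has no later Period 2 visit. Week 64 is missing, the preceding assessment is the flare, and LOCF carries it. The loss is 0 and the result stays at 69.8%.

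**Step 4: R0 excluded from Period 2.** Let u be the assumed share of flares found only at unscheduled visits. Lost flares = 67u, rounded. The last column applies if the affected subjects also leave the FAS.

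| u (assumed) | Flares lost | Counted as non-flares | Removed from the FAS |
|---|---|---|---|
| 5% | 3 | 64/96 = 66.7% | 64/93 = 68.8% |
| 10% | 7 | 60/96 = 62.5% | 60/89 = 67.4% |
| 20% | 13 | 54/96 = 56.2% | 54/83 = 65.1% |

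**Step 5: loss that exceeds the planned precision.** 8/96 = 8.3 points is below 9.2, and 9/96 = 9.4 points is above it. Nine flares are 9/67 = 13.4% of the expected total, counted as non-flares.

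**Step 6: scheduled-first route.** Each subject affected costs 1/96 = 1.0 point. The documents give no frequency, so no total is computed.

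**Step 7: FAS exposure.** In Appendix 2.3 the BASDAI/SADA windows end Week 24 at Day 182 and run without gaps from Day 183 to the end of Period 2. If assessments are placed by day, only a flare visit in about Days 169 to 182 would give no Period 2 evaluation. If R0 is wholly excluded, any subject who reaches R0 before another Period 2 visit is exposed.

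**The case against.** The best defence is that the SAP, read as a whole, already means cumulative flare. SAP 6.1.1.1 gives the time point as all of Period 2, whereas SAP 6.2.1 and 6.2.2 list scheduled visits for the secondary endpoints; a running count by visit fits that contrast. The protocol still calls for one percentage. LOCF expressly draws on unscheduled assessments. The R0 window (Day 1 or earlier, relative to retreatment) has the same form as the Period 1 baseline window, so it can define a baseline without removing the value from Period 2. SAP 3.4 and Appendix 2.1 point the same way. On this reading Step 3 applies and nothing is lost for subjects who enter Period 3.

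The override route is also thin. Protocol 6.5 makes retreatment optional, but no passage describes a flared subject who declines and continues Period 2 visits. Protocol 3.3 says that flaring subjects will enter retreatment, and Protocol 5.1 names flare as an example of a reason to discontinue. Protocol 3.3 and 6.5 should be reconciled with each other, but the proposed derivation works under either.

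Much of this stands, and it rules out a claim that flares are certainly lost. It does not supply the missing derivation. Both lines that tell the programmer what to produce are per visit, no row is named as primary, and no sentence says that an R0 value feeds the Period 2 flare table. The added Kaplan-Meier and Cox analysis uses no imputation, but its specified outputs are quartiles, plots and hazard ratios, not the 40-week proportion.

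**Conclusion.** The point holds as a mismatch between endpoint and analysis, together with an internal inconsistency on R0. The SAP does not turn any flare within 40 weeks into one subject-level proportion, and the result depends on a choice that it leaves open. The effect is zero for subjects entering Period 3 if R0 is a Period 2 value. If R0 is excluded, the planning result falls from 69.8% to between 66.7% and 56.2% for an assumed 5% to 20% of flares found only at unscheduled visits, or to between 68.8% and 65.1% if those subjects leave the FAS instead. The override route adds a loss of unknown, possibly nil, size.

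A reader might infer that the planned estimate is biased downward, perhaps severely: with half of all flares lost it would be 33/96 = 34.4%. The documents do not support that. It needs complete exclusion of R0, which SAP 3.4 and Appendix 2.1 speak against, and a 50% share that appears nowhere. This should be fixed before programming; it is not a demonstrated error in the result.

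**What to change.** 1. In SAP 6.1.1.1, define flared by visit v as ASDAS ESR at or above 2.1 at any assessment (scheduled, unscheduled, early discontinuation or pre-dose R0) after withdrawal and before the first retreatment dose. Once flared, a subject stays flared in all later rows.
2. Name the cumulative Week 64 n/N with its 95% CI as the primary estimate. Keep the by-visit table as cumulative support.
3. In Appendix 2.3 and SAP 4.1.2, state that pre-dose R0 data are both the last Period 2 assessment and the Period 3 baseline, and that they count for Period 2 FAS membership.

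The cost is SAP wording and one derivation flag. No new data are needed, and no visit or treatment rule changes.

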2.1. Study Objectives

2.1.1. Primary Objective

- To estimate the proportion of subjects who flare within 40 weeks following withdrawal of ETN in subjects who have achieved ASDAS CRP less than 1.3 (inactive disease).

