4. ANALYSIS SETS

4.1. Full Analysis Set

4.1.1. Period 1

The full analysis set for period 1 will include all subjects who took study medication and had one evaluation after baseline.

4.1.2. Period 2

The full analysis set for period 2 will include all subjects who had at least one evaluation during period 2.

4.1.3. Period 3

The full analysis set for period 3 will include all subjects who took study retreatment medication and had at least one evaluation after restarting active therapy.

4.2. 'Per Protocol' Analysis Set

A per-protocol population may be defined for sensitivity analysis of the primary and key secondary efficacy endpoints (ASDAS inactive disease, ASAS 40). This will be defined separately for the withdrawal and retreatment periods. The per-protocol populations will be defined as subsets of each FAS population excluding subjects who have a protocol violation that is thought to potentially affect efficacy, with focus on potential violations of inclusion criteria in each period. There will be no per protocol population defined for period 1 of the study.

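### The Week 64 flare proportion counts subjects who leave Period 2 unflared as non-flares, and the planned Kaplan-Meier outputs list no 40-week flare probability with a confidence interval to set beside it

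*SAP*

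**What the plan says.** The primary objective (SAP 2.1.1) is "To estimate the proportion of subjects who flare within 40 weeks following withdrawal of ETN". Protocol 9.2.1 says that flare in Period 2 "will be summarized descriptively as the percent with flare with 95% confidence interval".

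SAP 6.1.1.1 turns this into "Analysis time points: Period 2 (over entire period"), with "method of imputation for missing data: LOCF" and the output "Descriptive: proportions (n/N) and 95% Confidence interval) at each period 2 visit". The analysis set (SAP 4.1.2) is "all subjects who had at least one evaluation during period 2". SAP 5.3 gives the carry-forward rule: "If the scheduled assessment is missing, the immediately preceding assessment, scheduled or unscheduled, will be used".

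Under additional analyses for the primary endpoint, SAP 6.1.1.1 plans a Kaplan-Meier (KM) analysis without imputation. It lists "Kaplan-Meier estimates of 25%, median and 75% survival and 95% confidence intervals", plus a plot of both studies. Protocol 9.2.2 lists only the KM median. SAP 5.2.4 adds a life table for comparing this study with B1801031. SAP 6.3.2 and 6.5.2 tabulate discontinuations by period and reason.

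SAP 2.2.3 foresees unflared exits: a subject who worsens without meeting the flare criterion may, on the investigator's judgement, leave for other treatment.

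**The concern.** Once such a subject has had one Period 2 evaluation, they are in the denominator for good. If the last ASDAS ESR is below 2.1, that value is carried to every later visit and the subject is a non-flare at Week 64, however early they left. The objective asks how many flare within 40 weeks. The analysis counts how many were seen to flare before leaving or before Week 64. The two agree only if no unflared leaver would have flared by Week 64; otherwise the count is the lower. The confidence interval uses the full N, as though everyone had been followed to the end.

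This is the trial's main number. The study has a single arm and a stated focus on estimation, so no concurrent control shares the error and cancels it. The planned KM analysis could supply a censoring-adjusted figure, but the 40-week value with an interval is not among its listed outputs.

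**Working it through.** **Inputs from the documents (Protocol 9.1, 3.2 and Schedule of Activities).** n = 96 entering withdrawal; 70% expected to flare; 40 weeks of follow-up; Period 2 visits 4, 8, 16, 24, 32 and 40 weeks after withdrawal.

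**Assumptions, because the documents give none.** Constant flare hazard; constant dropout hazard independent of flare; dropout by 40 weeks in the absence of flare d = 5%, 10% or 20%.

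**The plan's own figure.** Half-width = 1.96 × √(0.70 × 0.30 / 96) = 0.0917, or 9.2 points, in line with the roughly 10% in Protocol 9.1.

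**Expected Week 64 proportion.** Flare hazard λ = −ln(0.30)/40 = 0.0301 per week; dropout hazard μ = −ln(1 − d)/40.

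- Counted as flare: F = λ/(λ+μ) × [1 − exp(−40(λ+μ))]
- Left unflared: L = μ/(λ+μ) × [1 − exp(−40(λ+μ))]

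For d = 10%, μ = 0.00263, λ/(λ+μ) = 0.9195 and the bracket is 1 − 0.30 × 0.90 = 0.73. So F = 0.671 and L = 0.059.

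| d | Leave unflared, of 96 | Expected proportion | Bias (points) | Coverage of 70%: Wald / Clopper-Pearson / Wilson |
|---|---|---|---|---|
| 5% | 2.8 | 68.6% | −1.4 | 95.0 / 95.7 / 93.7% |
| 10% | 5.6 | 67.1% | −2.9 | 92.6 / 92.9 / 89.7% |
| 20% | 11.4 | 64.1% | −5.9 | 80.5 / 80.6 / 74.3% |

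Coverage is exact binomial with n = 96. Three interval methods are shown because the SAP names none. With no dropout they give 95.4%, 96.6% and 95.5%.

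**Reading this against a disposition table.** The percentages d are latent: at d = 20% only 11.9% actually leave unflared, because many flare first. The bias is about half the fraction that actually leaves unflared (for example 2.9 / 5.9 = 0.49). It reaches half the planned half-width (4.6 points) at d ≈ 16%, where L = 0.093, or 9.0 of 96. If 20% actually left unflared, the same model gives a shortfall of 10.1 points.

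**What the listed KM outputs show.** Under the same λ, survival reaches 75%, 50% and 25% at −ln(0.75)/λ = 9.6, −ln(0.50)/λ = 23.0 and −ln(0.25)/λ = 46.1 weeks. The last falls after Period 2 ends. A reached median with an unreached 25% survival time places the flare probability only between 50% and 75%.

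**What the added output would show.** Simulating the visit schedule with independent exits, with and without an assessment at exit, 1 − KM at 40 weeks averages 70.0% to 70.6%. The half-width is 9.1 to 9.7 points and coverage is about 95%.

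**If exits are informative.** Each unflared leaver can hide at most 1/96 = 1.04 points. If all of them would have flared, the truth is F + L = 71.5%, 73.0% or 76.0%. The proportion is then low by 2.9, 5.9 or 11.9 points, and KM (70%) by 1.5, 3.0 or 6.0.

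**The case against.** The strongest reply is that the plan already handles most of this. The KM analysis without imputation is filed under the primary objective; the curve's height at 40 weeks is the adjusted estimate; the life table works by visit window; and disposition by reason will show how many left unflared. The design also limits such exits. Subjects can be assessed at any time (Protocol 3.3), and the early discontinuation visit collects ESR, BASDAI and the subject's global assessment (Protocol 6.7), so anyone at or above 2.1 on leaving should count as a flare. All of this stands, and it makes the point an output to add rather than a wrong analysis. It does not close the gap: a height read off a plot has no stated interval, the life table is there for the between-study comparison, and an exit visit cannot see a later flare.

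A reader might infer three stronger things that the documents do not support.

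- **That LOCF itself is the fault.** A plain count of ever-flared over N gives the same Week 64 figure, provided a flare once met is carried as a flare. That proviso matters because retreatment is offered as an option (Protocol 6.5) and SAP 5.3 uses an available scheduled value, so a flared subject who stayed on visits and later scored below 2.1 could be counted differently. The issue is the absence of a censoring adjustment.
- **That the primary estimate will be materially wrong.** No dropout rate is given, and at 5% or 10% latent dropout the bias is well inside the half-width.
- **That unflared leavers who worsened should be called flares.** SAP 2.2.3 describes them as not meeting the criterion, so this would widen the endpoint.

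**Conclusion.** The point holds as a cheap improvement to the reported outputs. As far as unflared exits go, the Week 64 n/N is on average at or below the 40-week flare probability, never above it. Under 70% true flare, n = 96 and constant independent hazards, the shortfall is 1.4, 2.9 or 5.9 points when about 3, 6 or 11 subjects leave unflared. It is minor below roughly 9 of 96. Whether that number will be reached cannot be judged from the documents, which is a reason to list the adjusted estimate before dropout is known. The direction of the error needs no hazard assumption; its size does.

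**What to change.** Keep the percent with flare as the primary summary. In SAP 6.1.1.1, under the KM estimation outputs, add 1 − KM at 40 weeks after withdrawal with a 95% CI, in the Period 2 full analysis set, and report it next to the percent with flare. Use one visit-time convention throughout the time-to-flare data, so that Week 64 assessments made within their window count toward the 40-week estimate.

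State the limitation with it: KM assumes that exits are unrelated to flare risk, and it too is low if subjects at higher risk leave. An optional upper bound that counts every unflared leaver as a flare (1.04 points each at n = 96) can accompany it, labelled as a bound, with the flare definition unchanged.

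The cost is one output line from an analysis already planned, plus one more if the bound is included. Protocol Section 9 calls for a protocol amendment only for major changes to the primary endpoint definition or its analysis. Neither changes here, so a SAP edit is enough.
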